### 13.1.3 Sensitivity analysis

Additional sensitivity analyses will be performed to assess the robustness of primary analysis results with respect to handling of missing data. Sensitivity analyses will include the imputation of missing pain intensity scores using different pattern mixture models (PMMs).

Diligent attempts will be made to limit the amount of missing data in the primary efficacy endpoint. Efforts will be made to follow-up subjects who discontinue treatment and to collect the primary efficacy endpoint for the statistical analysis.

### Missingness assumptions – considerations

The primary analysis using the MMRM is based on the Missing at Random (MAR) assumption. For the treatment policy or de facto estimand, the MAR assumption is justified for neridronic acid

owing to the long half-life in bone and the anticipated persistent effect over the 12-week trial period. It can be assumed that the effect of neridronic acid continues after the treatment period is completed, and it also persists after the treatment period regardless of trial completion or early discontinuation. Therefore, the response of discontinued subjects will not change if the subjects continue to receive the stable therapy that they receive during the 12-week trial period up to Visit 8. If subjects change their treatment after discontinuation from the trial, it is nevertheless reasonable to assume that their response is not significantly altered as there are currently no established effective treatments. Hence, the MAR assumption is considered a plausible missingness mechanism for the primary estimand in the case of neridronic acid.

The MAR assumption cannot be verified based on data observed in the trial. Deviations from MAR cannot be excluded and several plausible missing not at random (MNAR) assumptions will be investigated to assess their impact. MNAR assumptions will be defined via pattern mixture models (PMM) specifying the distribution of missing values, e.g., for subjects discontinuing before the end of the trial. Plausible PMMs for the primary estimand are placebo multiple imputation (PMI) and the delta shift method.

PMI is a reference-based approach based on the copy reference method. It models the means of missing values in the active arm based on the means observed in the placebo arm (reference arm). The method assumes that the response of discontinued subjects in the active arm gradually approaches the response in the placebo arm and eventually no effect of neridronic acid persists after a subject discontinues. For neridronic acid this appears conservative in light of the anticipated persistent effect.

The delta shift method models the means of missing values in the active arm by adding a pre-specified value  $\Delta$  to the observed means in the active arm. The method includes a tipping point analysis, which is defined as the delta that must be added in order to overturn conclusions from the primary analysis from statistically significant to statistically insignificant. The method assumes that discontinued subjects in the active arm have higher pain compared to subjects who stay in the trial. Again this seems conservative if persistence of effect can be assumed for neridronic acid.

Overall, the 2 PMMs can be considered more conservative than MAR because they model missing pain intensity scores in the active arm using higher mean values than the means actually observed, whereas the placebo arm is not changed. In this way, neridronic acid is effectively penalized under these assumptions.

In summary, for neridronic acid the MAR assumption seems to be the most plausible missingness assumption for analyses estimating the primary estimand. It will be supplemented by sensitivity analyses based on MNAR assumptions representing plausible and reasonably conservative deviations from MAR.

### **Sensitivity analysis**

Sensitivity analyses will be conducted with two imputation methods followed by an analysis of covariance (ANCOVA) model. The ANCOVA model will be fitted to the change from baseline in the average pain intensity scores at Week 12 recorded once daily in the electronic diary, with the covariate baseline pain intensity score, and the factors geographic region and treatment as fixed effects.

The results of the primary analysis and both sensitivity analyses will be summarized numerically and graphically in a forest plot, presenting the number of subjects, model estimates and 95% CIs of the treatment differences to placebo for both active doses.

The primary efficacy analysis will use the observed values of the primary efficacy endpoint without any imputations. To perform the sensitivity analyses for the primary analysis, weekly average pain intensities of the primary efficacy endpoint will be imputed until Week 12.

In the following the concept of PMM will be described as well as the details on the specific PMM imputation information for PMI and the delta shift method.

### **Pattern mixture models**

Subjects dropping out will be classified into patterns according to the week they discontinue from the trial. In each pattern, the distribution of missing values conditional on observed values is determined based on the imputation method used and imputations are drawn from the modified distribution.

The pattern mixture model framework (e.g., Verbeke and Molenberghs 2009) will be implemented using multiple imputation. Multiple imputation comprises 3 separate steps:

1. **Impute:** Generate  $M$  completed datasets (week 1 to week 12) drawing imputed values from the pattern-specific distributions. In total  $M = 200$  imputations will be generated. This is in line with recommendations in Carpenter and Kenward (2013).
2. **Analyze:** Analyze the  $M$  completed datasets individually (analysis via ANCOVA).
3. **Combine:** Combine the results from the  $M$  individual analyses into a single result using Rubin's rules (Little and Rubin 2002).

The imputation model will be based on the Markov chain Monte Carlo (MCMC) method for general patterns of missingness (Dmitrienko et al. 2005).

The imputations step 1. is described for both PMM used in this trial in the below with the specific imputation used.

All missing values will be imputed in the same way, i.e., no differentiation between intermittent missing values and missing values after dropout is made. Missing values will be imputed for all 12 weeks.

#### *Placebo Multiple Imputation*

The Placebo Multiple Imputation method draws imputations in all treatment arms based on the data observed in the placebo arm. In each pattern, the distribution of missing values conditional on observed values is defined for all arms by the corresponding distribution from the placebo arm. The imputation step will be performed as follows:

- a. Estimate  $M$  sets of parameters for the pattern specific reference distribution from the placebo arm. All  $M$  parameter datasets will be stored in an analysis dataset.
- b. Generate  $M$  completed datasets for all treatment arms using the  $M$  sets of parameters from step 1. All  $M$  imputed datasets will be stored in an analysis dataset.

#### *Delta Shift Method*

The Delta Shift Method is based on the observed distribution and shifts the observed means at the time points after dropout by a pre-specified value. In each pattern, the distribution of missing values

conditional on observed values is based on the shifted means, and imputations are drawn from the modified distribution. This approach models a diminishing placebo effect after a subject drops out.

The sensitivity analysis will use different values for the shift parameter  $\Delta$ . Delta will start with 0 and be increased by 0.1 points until the tipping point has been reached. The tipping point is defined as the delta that must be added in order to overturn conclusions from the primary analysis from statistically significant to statistically insignificant. Starting with 0 enables to evaluate MI under the MAR assumption.

The shift parameter is constant, i.e., the same shift parameter will be used for all treatment arms, for all times after dropout, and for all patterns. Based on this, the imputation step will be performed as follows:

- a. Estimate  $M$  sets of parameters of the linear model. All  $M$  parameter datasets will be stored in an analysis dataset.
- b. Generate  $M$  completed datasets using the  $M$  sets of parameters from step 1.
- c. Modify the completed datasets by adding a shift  $\Delta$  to each imputed value. All  $M$  imputed datasets will be stored in an analysis dataset.

All missing values will be imputed in the same way, i.e., no differentiation between intermittent missing values and missing values after dropout is made.

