The delta shift method models the means of missing values in the active arm by adding a pre-specified value Δ to the observed means in the active arm. The method includes a tipping point analysis, which is defined as the delta that must be added in order to overturn conclusions from the primary analysis from statistically significant to statistically insignificant. The method assumes that discontinued subjects in the active arm have higher pain compared to subjects who stay in the trial. Again this seems conservative if persistence of effect can be assumed for neridronic acid.

Overall, the 2 PMMs can be considered more conservative than MAR because they model missing pain intensity scores in the active arm using higher mean values than the means actually observed, whereas the placebo arm is not changed. In this way, neridronic acid is effectively penalized under these assumptions.

In summary, for neridronic acid the MAR assumption seems to be the most plausible missingness assumption for analyses estimating the primary estimand. It will be supplemented by sensitivity

analyses based on MNAR assumptions representing plausible and reasonably conservative deviations from MAR.

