The delta shift method models the means of missing values in the active arm by adding a pre-specified value Δ to the observed means in the active arm. The method includes a tipping point analysis, which is defined as the delta that must be added in order to overturn conclusions from the primary analysis from statistically significant to statistically insignificant. The method assumes that discontinued subjects in the active arm have higher pain compared to subjects who stay in the trial. Again this seems conservative if persistence of effect can be assumed for neridronic acid.

Overall, the 2 PMMs can be considered more conservative than MAR because they model missing pain intensity scores in the active arm using higher mean values than the means actually observed, whereas the placebo arm is not changed. In this way, neridronic acid is effectively penalized under these assumptions.

In summary, for neridronic acid the MAR assumption seems to be the most plausible missingness assumption for analyses estimating the primary estimand. It will be supplemented by sensitivity analyses based on MNAR assumptions representing plausible and reasonably conservative deviations from MAR.

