## **7 DOCUMENT AND CHANGE HISTORY**

### **7.1 Changes in analysis compared to the trial protocol**

Not applicable.

Change from protocol	Rationale for change

Section 1.2 Trial objectives, endpoints, and outcomes
 
Other data to be collected that are not directly attributed to or considered as an endpoint
 
 
• Change from baseline to Week 6, Week 12, Week 26, Week 28, Week 36, and Week 52 in the responses to questions on the following questionnaires (recorded on the tablet computer): 
 
– Patient-Reported Outcomes Measurement Information System (PROMIS®)-29 profile version 2.0 (PROMIS-29 profile) (sub-scores: physical function, anxiety, depression, fatigue, sleep disturbance, social roles and activities, and pain interference). The change from baseline to Week 16 and Week 22 will be assessed for question number 29, GLOBAL07 only.
 
– Question EDDEP39 of the PROMIS Item Bank version 1.0 – Emotional Distress – Depression (PROMIS-EDDEP39) (not for Week 28).
 
– The 6 neuropathic pain items of the Short-Form McGill Pain Questionnaire 2 (SF-MPQ-2) (single items and the combined score).
 
– Pain Catastrophizing Scale (PCS) (not for Week 28).
 
– Pain Self Efficacy Questionnaire (PSEQ) (not for Week 28).
 
 
 
	
Schedule of events in protocol shows that these assessments are not done at Week 28.

Protocol Section 14.1.7.2 Analysis of the secondary endpoints
 
A logistic regression model will be fitted to the data, including the covariate baseline pain intensity score, and the factors geographic region, week, and treatment, and treatment-by-week interaction as fixed effects.
	
Change to logistic regression at respective weeks instead of longitudinal analysis to simplification of model fitting.

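### The SAP's delta-shift rule worsens imputed pain scores in both arms, where the protocol worsens only the active arm; the tipping point will look more robust than the protocol's method would show

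*SAP*

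**What the plan says.** **Protocol.** Sections 1.5.3.3 and 14.1.7.3 describe the same method. The delta shift "models the means of missing values in the active arm by adding a pre-specified value", and the tipping point is the delta at which the primary result stops being significant. Both sections say that placebo is left as it is, and conclude: "In this way, neridronic acid is effectively penalized under these assumptions".

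**SAP rationale.** The considerations text in SAP 13.1.3 repeats this. Both pattern mixture models are called more conservative than MAR because they model missing active-arm scores "using higher mean values than the means actually observed, whereas the placebo arm is not changed".

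**SAP operating rule.** The Delta Shift Method text, later in the same section, is what a programmer would code from. It states that "the same shift parameter will be used for all treatment arms, for all times after dropout, and for all patterns". Step c reads "Modify the completed datasets by adding a shift" and applies the shift to every imputed value, with no restriction by arm. The reason given is also different: "This approach models a diminishing placebo effect after a subject drops out". Delta starts at 0 and rises in steps of 0.1 until significance is lost.

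**Declared changes.** SAP 7.1 lists two departures from the protocol. One concerns questionnaires not collected at Week 28. The other concerns the responder model ("Change to logistic regression at respective weeks instead of longitudinal analysis to simplification of model fitting"). The delta shift is not listed.

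**The concern.** The operating rule cannot be reconciled with the protocol or with the SAP's own justification for the method. A delta analysis is a stress test of the drug only if it worsens the drug arm relative to placebo. If the same amount is added to missing scores in both arms, most or all of the relative penalty disappears, and it reverses when placebo has more missing data.

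The tipping point is one of two planned checks of the primary result against departures from MAR, an assumption both documents concede cannot be verified from the trial data. A tipping point produced under the operating rule but presented with the rationale's wording would overstate how much departure from MAR the result can withstand.

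**Working it through.** **Inputs from the documents** (Protocol 1.5.1, SAP 5.2): difference -1.0, SD 2.0, one-sided alpha 0.025, 86 per arm for 90% power, 90 per arm planned. The plan's own figure reproduces: noncentral-t power is 0.8999 at 85 per arm and 0.9032 at 86.

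**Assumed input.** No missingness rate is given. Shares with an imputed Week 12 score, m_A (active) and m_P (placebo), are therefore varied.

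**Estimate.** With the observed difference set at the planned value:

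- active-only shift: -1.0 + delta × m_A
- all-arms shift: -1.0 + delta × (m_A - m_P)

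**Variance.** [2·SD² + m_A(1-m_A)·delta² + m_P(1-m_P)·delta_P²]/90, plus between-imputation variance SD²·[1/(90(1-m)) - 1/90] summed over the arms. Here delta_P is 0 for the active-only rule and delta for the all-arms rule. The result tips when estimate/SE rises above -1.96.

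**Worked case, 15% missing in each arm.** The part of the variance that does not depend on delta is 8/90 + 2 × 4 × (1/76.5 - 1/90) = 0.0889 + 0.0157 = 0.1046.

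- Active-only, delta 2.3: estimate -1.0 + 0.345 = -0.655; variance 0.1046 + 0.1275 × 5.29/90 = 0.1121; SE 0.335; z = -1.957. Tips (z at 2.2 is -2.007).
- All arms, delta 2.3: estimate still -1.0; SE 0.346; z = -2.89. Far from tipping.
- All arms, delta 7.5: estimate still -1.0; variance 0.1046 + 2 × 0.1275 × 56.25/90 = 0.2640; SE 0.514; z = -1.946. Tips (z at 7.4 is -1.962), through variance inflation alone.

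**Tipping delta over a range of missing shares:**

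| Missing active / placebo | Active-only (protocol) | All arms (SAP rule) |
|---|---|---|
| 5% / 5% | 6.7 | not reached by 10 |
| 10% / 2% | 3.6 | 4.2 |
| 10% / 10% | 3.5 | 9.0 |
| 15% / 15% | 2.3 | 7.5 |
| 20% / 20% | 1.7 | 6.5 |
| 15% / 10% | 2.4 | 4.7 |
| 20% / 10% | 1.8 | 3.0 |
| 10% / 15% | 3.5 | not reached by 10 |
| 10% / 20% | 3.4 | not reached by 10 |
| 5% / 15% | 6.4 | not reached by 10 |

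At 10%/20% the all-arms shift strengthens the apparent effect: at delta 3.4 the estimate is -1.0 + 3.4 × (0.10 - 0.20) = -1.34.

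**Does the direction depend on the shares chosen?** For small m_P, shifting placebo moves the estimate in the drug's favour by delta × m_P. It also raises the SE by about m_P × delta²/(2 × 90 × SE). The first outweighs 1.96 times the second whenever delta < 2 × 90 × √(8/90)/1.96 = 27.4, well beyond a 0–10 scale. Over all pairs of shares from 1% to 40% in 1% steps, active-only tips at a delta above 0 and up to 10 in 1,510 pairs. In those, all-arms tips later in 1,488 (606 of them not by 10), at the same step in 22, and earlier in none. These are counts of grid points, not probabilities.

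**Simulation check.** Settings were M = 200, Rubin's rules, 0.1 steps, a search to 10, 150 significant runs per scenario, and an assumed correlation of 0.8 between an earlier observed week and Week 12. Median tipping deltas, active-only v all arms:

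- 10%/10%: 3.6 v 9.3
- 15%/15%: 2.7 v 8.2
- 20%/20%: 2.3 v 7.6
- 20%/10%: 2.1 v 3.5
- 10%/20%: 3.8 v not reached in any run

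With an assumed correlation of 0.5, 15%/15% gives 2.8 v 8.35.

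**The case against.** The strongest reply is that this is an editing slip and not a change of method. SAP 13.1.3 also says placebo is unchanged, and its sensitivity text refers to more than one active dose in a trial that has only one, which suggests wording carried over from elsewhere. That may well explain the origin. It does not settle which rule would be run: step c and the sentence about a waning placebo effect both fit a shift that includes placebo, and code would follow the operating rule.

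The size of the effect rests on assumed missing shares, which may prove small. One diary rating is enough for a weekly score (SAP 13.1.1), and subjects who stop treatment are encouraged to stay in follow-up (Protocol 9.3.1 and 9.3.2). This stands. At 5%/5% both rules indicate robustness, and with little placebo missingness (10%/2%) the gap is small. The rules coincide when placebo has no imputed Week 12 values.

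An all-arms shift is also a coherent MNAR scenario in itself. The defect is that it is not the scenario described, justified or declared.

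The SAP cites the protocol of 14 March 2018, and the supplied protocol includes Amendment 01. The amendment log as supplied lists no change to section 1.5.3.3 or 14.1.7.3, so the version gap does not explain the difference.

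**Conclusion.** The concern holds and should be fixed. The SAP's operating rule contradicts the protocol and the SAP's own rationale, and SAP 7.1 does not declare it. Followed as written, it gives a tipping point never earlier than the protocol's method over the grid examined, and usually much later. With balanced missingness of 10% to 20% the tipping delta is roughly 2.5 to 4 times as large (9.0/3.5 = 2.6; 6.5/1.7 = 3.8). With heavier placebo missingness the analysis may never tip. With heavier active missingness a reduced penalty remains.

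The direction needs only some imputed placebo values at Week 12. The size depends on the assumed shares, an observed difference equal to the planned -1.0, SD 2 and 90 per arm. The consequence is bounded: the primary MMRM, type I error, sample size and the placebo multiple imputation check are untouched, and no decision rule is attached to the tipping point.

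**What to change.** In SAP 13.1.3, Delta Shift Method:

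- Restrict the shift, including step c, to imputed values in the neridronic acid arm. Impute placebo values under MAR and leave them unshifted.
- Delete the sentence on a diminishing placebo effect.
- End the search at the limit of the pain scale and report the tipping point as not reached if significance is never lost.
- Say whether intermittent gaps are shifted. The text speaks of a shift after dropout but also says that "no differentiation between intermittent missing values and missing values after dropout is made". This is a separate ambiguity, best settled in the same edit.

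If an all-arms shift, or a two-way grid of separate active and placebo deltas, is wanted, declare it in SAP 7.1 with a rationale, in addition to the active-only analysis.

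The cost is SAP wording and one line of imputation code before unblinding, with no effect on patients or data collection. The sponsor's only downside is a less favourable reported tipping point.

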## **13.2 Secondary endpoints**

All secondary efficacy endpoints will be analyzed for the Full Analysis Set.

Descriptive summaries will be generated for all visits where data is assessed as per schedule of events in Section 1.7 of the protocol. Analysis will be presented per visit and treatment if not specified differently.

### **13.2.1 Average pain intensity (recorded on tablet computer)**

The change from baseline in the average pain intensity, recorded on the tablet computer, will be analyzed with an MMRM, including the covariate baseline pain intensity score, and the factors geographic region, week, treatment, and treatment-by-week interaction as fixed effects, and subject as random effect. An unstructured covariance matrix will be used to model the covariance structure.

The analysis will be performed using the contrast, i.e., the mixed model Wald test, of 400 mg neridronic acid versus placebo at Week 26 of the treatment, week and treatment-by-week interaction term of the mixed effects model described above. Model-based parameter estimates, standard errors, 95% confidence intervals, and p-values will be tabulated. This analysis will be performed using the observed values without imputation of missing values.

### **13.2.2 Pain response to treatment (recorded on tablet computer)**

Pain response to treatment, defined as an at least 30% decrease from baseline in average pain intensity, recorded on the tablet computer, will be derived. If a subject shows a worsening or the pain intensity score for the respective visit is missing, then the subject will be considered a pain non-responder for the respective visit. A logistic regression model will be fitted to the data, including the covariate baseline pain intensity score, and the factors geographic region and treatment as fixed effects. Model-based parameter estimates, standard errors, 95% confidence

intervals, and p-values for the odds ratio at Week 12 and Week 26 between 400 mg neridronic acid and placebo will be tabulated.

The analysis of pain response to treatment will include a cumulative responder analysis at Week 12, Week 26, and Week 52, where responder rates will be calculated for different percentage thresholds for decrease from baseline in average pain intensity. The evaluation of Week 52 assessments is part of other data that is collected but due to similar analyses described together with secondary endpoint evaluations at Week 12 and Week 26.

The percentage decrease from baseline in average pain intensity, recorded on the tablet computer, will be derived per subject as

$$\% \text{pain decrease} = \frac{\text{Baseline Pain Intensity} - \text{average pain intensity Week } x}{\text{Baseline Pain Intensity}} \times 100$$

with  $x$  being Week 12, Week 26, and Week 52 respectively.

The responder rate for a given percentage threshold is defined as the proportion of subjects with a % pain decrease equal to or above the percentage threshold, i.e. the 30% responder rate (30% responder) is the percentage of subjects with at least 30% pain decrease. The distribution (by changing the percentage threshold) of responder rates in a given week will be determined for each treatment group using percentage thresholds of 0, 10, 20, 30, 40, 50, 60, 70, 80, 90, and 100. Descriptive statistics will be displayed for those percentage thresholds as well as for non-responders.

In addition, 30% responders and 30% non-responders (subject who show a worsening or for whom the pain intensity score is missing and subjects with pain decrease <30%) will be displayed for Week 12, Week 26, and Week 52.

A graphical presentation for Week 12, Week 26 and Week 52 of the proportion of subjects defined as responders by treatment (y-axis) versus the threshold value (continuous scale) used to define a response (x-axis) will be produced. The 30% reduction as well as the 50% reduction will be indicated by vertical lines.

